5.1.3.4 Management of Increases in QT Interval

Study drug should be discontinued in patients who develop any of the following, unless there is a clear alternative cause for the changes:

- Sustained (at least two ECG measurements >30 minutes apart) QTcF that is >500 ms and >60 ms longer than the baseline value
- Sustained absolute QTcF that is >515 ms (or >530 ms for patients with a ventricularly paced rhythm)
- An episode of torsades de pointes or a new ECG finding of clinical concern

Of note, if there is a new intraventricular conduction block, the increase in QRS complex duration should be subtracted from the QTcF change, because this represents an increase in QTcF unrelated to alterations in repolarization. Also of note, it is not uncommon to record arrhythmias such as non-sustained ventricular tachycardia, supraventricular tachycardia, pauses, or atrial fibrillation in healthy volunteers receiving placebo during periods of extended ECG monitoring. Therefore, it is critical that expert cardiology advice be sought to confirm any ECG changes and to ascertain the likelihood of a drug-induced arrhythmia versus the background occurrence of this arrhythmia. In such a situation, saving all available ECG data is highly suggested.

Management of patients with sustained QTcF prolongation should include close monitoring, with ECGs repeated at least hourly until two successive ECGs show resolution of the findings, correction of any electrolyte abnormalities, and possible discontinuation of other concomitant medications that are known to prolong the QT interval, including other drugs used to treat severe COVID-19 pneumonia, such as chloroquine, hydroxychloroquine, azithromycin, lopinavir/ritonavir, etc.). Consultation with a cardiologist or electrophysiologist is recommended, to help in the management of such patients.

In rare circumstances, it may be acceptable to resume study drug, at a lower dose, provided that any ECG abnormalities have resolved and the patient is appropriately monitored. Clinical judgment should be applied.

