3.3 RATIONALE FOR STUDY DESIGN

3.3.1 Rationale for MSTT1041A (Anti-ST2) Dose and Schedule

For the MSTT1041A arm, 700 mg IV will be administered for the first dose. For patients who remain in hospital and on oxygen 2 weeks after the first dose (Day 15), a second dose of 350 mg IV will be administered.

The proposed dose is based on clinical experience in healthy subjects (safety, pharmacokinetics, and pharmacodynamics) observed in the SAD study (AMG Study 20110235) and in the MAD study (AMG Study 20110236), as well as in the Phase IIb study GB39242 in patients with severe asthma (safety, efficacy, pharmacokinetics, and pharmacodynamics). In Study 20110235, at least 3 subjects (per SC cohort) or at least 6 subjects (per IV cohort) received SC doses of MSTT1041A up to 420 mg or IV doses

MSTT1041A/UTTR1147A—Genentech, Inc.
37/Protocol GA42469, Version 4

of MSTT1041A up to 700 mg. In Study 20110236, at least 6 subjects per cohort received multiple SC or IV doses of MSTT1041A, Q2W or every 4 weeks (Q4W), up to 700 mg IV.

A small number of patients with mild asthma (n= 6) or chronic rhinosinusitis with nasal polyps (CRSwNP; n=1) were also enrolled in Phase I studies. MSTT1041A was well tolerated in Phase I studies, with no significant safety issues identified, including at the highest doses (700 mg IV of MSTT1041A administered as a single dose or Q4W for three doses). [REDACTED]

In Study GB39242, 502 patients with severe asthma were randomized in a 1:1:1:1 ratio to receive 1 of 3 doses of MSTT1041A (70 mg, 210 mg, or 490 mg SC) or placebo Q4W for 52 weeks, for a total of 13 doses. In this study, the 490 mg Q4W dose showed a significant reduction over placebo in incidence of asthma exacerbations and met the primary endpoint. MSTT1041A was well tolerated. Rates of adverse events were generally similar between the three treatment arms and the placebo arm, and were mostly mild or moderate in intensity. [REDACTED]

The available evidence suggests that circulating levels of the secreted soluble form of ST2 (sST2) are significantly increased in patients with ARDS compared with healthy subjects or patients with severe asthma. A median concentration of sST2 of 534 ng/mL has been reported in patients with ARDS (Alladina et al. 2016), [REDACTED]

As sST2 acts as a decoy to bind and inhibit released IL-33, higher sST2 concentrations in patients with ARDS suggest that higher doses of MSTT1041A may be required to achieve efficacy in ARDS compared with severe asthma.

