Based on the tolerability profile in patients with UC to date and a potential lower PK exposure in the target population, 90 µg/kg Q2W was chosen as the dose regimen with the highest benefit–risk ratio for patients with severe COVID-19 pneumonia. In patients randomized to UTTR1147A, 90 µg/kg IV will be administered on Day 1. For patients who remain hospitalized on supplemental oxygen on Day 15, a second dose at 90 µg/kg IV will be given. The first dose of 90 µg/kg is targeted to maximize the drug exposure in patients with severe COVID-19 pneumonia. The second dose is targeting the epithelial barrier repair and protective mechanisms to help patients with ongoing lung damage and pulmonary dysfunction.

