4.6 TREATMENT, PATIENT, STUDY, AND SITE DISCONTINUATION

4.6.1 Study Treatment Discontinuation

Patients must permanently discontinue study treatment if they experience any of the following:

- Any medical condition that the investigator or Sponsor determines may jeopardize the patient's safety if he or she continues to receive study treatment
- Investigator or Sponsor determination that treatment discontinuation is in the best interest of the patient
- Pregnancy
- Grade ≥ 4 dermatologic *reactions* (as described in Section 5.1.3.3)
- Major adverse cardiovascular event
- Hs-troponin I or T in the "intermediate" or "indeterminate" range or hs-troponin $>$ ULN to $< 5 \times$ ULN (and above baseline) AND either reduced ejection fraction or new hypokinesis by echocardiogram or evidence of myocarditis and/or pericarditis (as described in Section 5.1.3.3)
- Hs-troponin I or T at a level indicative of myocardial ischemia, $\geq 5 \times$ ULN, or category above "intermediate" or "indeterminate" (as described in Section 5.1.3.3)
- Conventional cardiac troponin I or T $>$ ULN, if high-sensitivity immunoassay is not available locally (as described in Section 5.1.3.3)
- QTcF prolongation or torsades des pointes as described in Section 5.1.3.4, unless there is a clear alternative cause for the changes
- Grade ≥ 3 infusion-related reaction as described in Section 5.1.3.3
- Use of prohibited therapy as described in Section 4.4.3

The primary reason for study treatment discontinuation should be documented on the appropriate eCRF. Patients who discontinue study treatment will not be replaced.

Patients will remain in study and complete all study visits and assessments (with the exception of the study drug administration).

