5.1.3 Management of Patients Who Experience Adverse Events

5.1.3.1 Dose Modifications

Dose modifications are not permitted in this study.

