5.1.3.2 Treatment Interruption

Treatment interruptions are not applicable in this study, as there are only two doses (see Section 4.6.1).

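### Section 5.1.3.4 lets study drug be resumed at a lower dose after QT findings, which conflicts with the ban on dose modifications (5.1.3.1) and, without a clear alternative cause, with permanent discontinuation (4.6.1)

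*Protocol*

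**What the plan says.** Section 5.1.3.4 lists the ECG events for which study drug should be stopped unless another cause is clear: two sustained QTcF thresholds, and "An episode of torsades de pointes or a new ECG finding of clinical concern". After a paragraph on managing sustained QTcF prolongation, it closes with: "In rare circumstances, it may be acceptable to resume study drug, at a lower dose, provided that any ECG abnormalities have resolved". The sentence goes on to require monitoring, and the section ends by leaving the matter to clinical judgment.

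Three other places govern the same decision.

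- Section 5.1.3.1: "Dose modifications are not permitted in this study". No exception is given.
- Section 5.1.3.2: "Treatment interruptions are not applicable in this study, as there are only two doses".
- Section 4.6.1: "Patients must permanently discontinue study treatment if they experience any of the following". The list that follows includes "QTcF prolongation or torsades des pointes as described in Section 5.1.3.4, unless there is a clear alternative cause for the changes".

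The scheduled doses are in Sections 3.3.1 and 3.3.2. MSTT1041A starts at 700 mg, and for patients still in hospital on oxygen at Day 15 "a second dose of 350 mg IV will be administered". UTTR1147A is 90 µg/kg on Day 1. "For patients who remain hospitalized on supplemental oxygen on Day 15, a second dose at 90" µg/kg IV is given, so its amount does not change.

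**The concern.** The permissive sentence sits where the decision is made. Section 4.5.7 sends an investigator who finds a prolonged QTcF after dosing to Section 5.1.3.4 to decide on discontinuation. An investigator who relies on its last paragraph could give a reduced dose that Section 5.1.3.1 forbids, in an amount the protocol does not define. Where no other cause is clear, that investigator would also be re-dosing a patient for whom Section 4.6.1 requires a permanent stop. What is at stake is patient safety and consistent conduct across sites after a serious cardiac signal. The statistical analysis is not affected.

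**Working it through.** No arithmetic beyond simple comparison applies. The check sets the sections side by side.

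**Step 1: which dose could be resumed.** The protocol has two doses (Section 5.1.3.2). If the event follows the first, 2 − 1 = 1 dose remains, on Day 15 (or on Day 14, 16 or 17 under Appendix 1, footnote c). If it follows the second, nothing remains. Resuming study drug therefore means, in practice, giving the Day 15 dose.

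**Step 2: what counts as a lower dose.**

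- UTTR1147A: Day 1 is 90 µg/kg and Day 15 is 90 µg/kg, a ratio of 90/90 = 100%. Any lower µg/kg dose is a departure from the schedule.
- MSTT1041A: Day 1 is 700 mg and Day 15 is 350 mg, a ratio of 350/700 = 50%. The scheduled second dose is already lower than the first and is not a modification. Only a dose below 350 mg departs from the schedule.

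**Step 3: against Section 5.1.3.1.** Any Day 15 dose below 90 µg/kg of UTTR1147A or below 350 mg of MSTT1041A is a dose modification. Section 5.1.3.4 would allow it and Section 5.1.3.1 does not, whatever the cause of the ECG change. This conflict is direct.

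**Step 4: against Section 4.6.1, for QTcF prolongation or torsades.**

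- No clear alternative cause: discontinuation is permanent, so any further dose conflicts, including the scheduled MSTT1041A 350 mg.
- Clear alternative cause: the QT item does not bar further dosing. The scheduled dose is allowed, and only a reduced one conflicts, through Step 3.

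The resumption sentence draws no such line. Its conditions are rarity, a resolved ECG and monitoring. Cause is not among them.

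**Step 5: whether an amount is given.** The dosing text in Sections 3.1.1, 3.3.1, 3.3.2 and 4.3.2 gives only the scheduled amounts. No reduced dose is stated for either drug.

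**Step 6: effect on the analysis.** A patient in this position has already had the Day 1 dose. That patient is therefore in the modified intent-to-treat population of Section 6, analysed as randomized, and stays in follow-up after stopping study drug (Section 4.6.1). Giving or withholding the Day 15 dose does not move anyone in or out of the comparison.

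**The case against.** The best defence is to read the sections together. The QT item in Section 4.6.1 refers to Section 5.1.3.4 and exempts a clear alternative cause, so the rare circumstances may be meant as just those exempted cases. This softens the conflict with Section 4.6.1, because the sentence can be read that way although it does not say so. It leaves the conflict with Section 5.1.3.1 intact, since a reduced dose is still a modification.

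A second defence is that the lower dose means the scheduled MSTT1041A 350 mg. That reading works for one drug where there is a clear alternative cause. It cannot serve UTTR1147A, and Section 5.1.3.4 does not distinguish the two drugs.

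Third, there are safeguards. The note to Figure 1 in Section 3.1.1 and Appendix 1, footnote w, both make the Day 15 dose conditional on Section 4.6.1. Section 4.5 requires a toxicity assessment before each dose, Section 4.5.7 requires notice to the Medical Monitor, and Section 5.1.3.4 calls for cardiology advice. These stand and lower the risk. They do not say what to do with a sentence that permits a dose another section forbids.

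A reader might also infer more than the text supports:

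- **That every resumption breaks a rule.** It does not. Scheduled MSTT1041A 350 mg after a clear alternative cause breaks none.
- **That sites are forced into a deviation.** They are not. The sentence is permissive, and an investigator who withholds the dose complies with every section.
- **That re-dosing after torsades is expressly allowed.** The sentence names no event and follows directly on text about sustained QTcF prolongation. The broad reading is open but not required.
- **That Section 4.6.1 is defective because its QT item omits a new ECG finding of concern.** Its general patient-safety item can cover such a finding, and making it an automatic permanent stop would be new policy.

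**Conclusion.** The point holds. The last paragraph of Section 5.1.3.4 contradicts Section 5.1.3.1 for any dose below the scheduled Day 15 dose. Because it is not restricted by cause, it also contradicts Section 4.6.1 for QTcF prolongation or torsades without a clear alternative cause. The first conflict is direct. The second depends on taking the sentence as written, without an implied limit to the exempted cases.

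The reach is small. The protocol gives no rate for these events. A patient must meet a Section 5.1.3.4 criterion, still be in hospital on supplemental oxygen, and have a resolved ECG within the second-dose window. At most one further dose per patient is involved, and no estimate, power or error rate changes. The point is worth correcting because it concerns cardiac safety and the correction is nearly free.

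The statement that no reduced dose is defined applies to the protocol alone. The pharmacy manual, to which dose preparation is delegated, is not at hand.

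**What to change.** Replace the resumption sentence at the end of Section 5.1.3.4 with:

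> Where there is a clear alternative cause (Section 4.6.1), the Day 15 dose, if otherwise due, may be given at the scheduled protocol dose once all ECG abnormalities have resolved and with appropriate monitoring of the patient. Reduced doses are not permitted (Section 5.1.3.1).

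This brings the three sections into line. Simply deleting the sentence would be worse, because the condition that the ECG has resolved before re-dosing would go with it. Sections 4.6.1 and 5.1.3.1 need no change, and the existing wording on cardiology advice can stay.

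The cost is one sentence in an amendment or clarification letter, with no effect on sample size or analysis. The downside is that investigators lose a discretionary reduced-dose option, though one that the protocol never defined.

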5.1.3.5 Anaphylaxis

Refer to [Appendix 3](#) for guidelines on anaphylactic precautions. These guidelines are intended as a reference and should not supersede pertinent local or institutional standard operating procedures.

In accordance with local guidelines, the measurement of tryptase (serum or plasma) and histamine (plasma) levels should be considered to support a diagnosis of anaphylaxis, although clinicians should treat anaphylaxis regardless of the availability of the results of these tests.

During the study, all anaphylaxis events should be accurately reported on the appropriate eCRF.

MSTT1041A/UTTR1147A—Genentech, Inc.
65/Protocol GA42469, Version 4

5.2 SAFETY PARAMETERS AND DEFINITIONS

Safety assessments will consist of monitoring and recording adverse events, including serious adverse events and adverse events of special interest, performing protocol-specified safety laboratory assessments, measuring protocol-specified vital signs, and conducting other protocol-specified tests that are deemed critical to the safety evaluation of the study.

Certain types of events require immediate reporting to the Sponsor, as outlined in Section [5.4](#).

5.2.1 Adverse Events

According to the ICH guideline for Good Clinical Practice, an adverse event is any untoward medical occurrence in a clinical investigation subject administered a pharmaceutical product, regardless of causal attribution. An adverse event can therefore be any of the following:

- Any unfavorable and unintended sign (including an abnormal laboratory finding), symptom, or disease temporally associated with the use of a medicinal product, whether or not considered related to the medicinal product
- Any new disease or exacerbation of an existing disease (a worsening in the character, frequency, or severity of a known condition) (see Sections [5.3.5.10](#) and [5.3.5.11](#) for more information)
- Recurrence of an intermittent medical condition (e.g., headache) not present at baseline
- Any deterioration in a laboratory value or other clinical test (e.g., ECG, X-ray) that is associated with symptoms or leads to a change in study treatment or concomitant treatment or discontinuation from study drug
- Adverse events that are related to a protocol-mandated intervention, including those that occur prior to assignment of study treatment (e.g., screening invasive procedures such as biopsies)

5.2.2 Serious Adverse Events (Immediately Reportable to the Sponsor)

A serious adverse event is any adverse event that meets any of the following criteria:

- Is fatal (i.e., the adverse event actually causes or leads to death)
- Is life threatening (i.e., the adverse event, in the view of the investigator, places the patient at immediate risk of death)

This does not include any adverse event that, had it occurred in a more severe form or was allowed to continue, might have caused death.

- Requires or prolongs inpatient hospitalization (see Section [5.3.5.12](#))

- Results in persistent or significant disability/incapacity (i.e., the adverse event results in substantial disruption of the patient's ability to conduct normal life functions)
- Is a congenital anomaly/birth defect in a neonate/infant born to a mother exposed to study drug
- Is a significant medical event in the investigator's judgment (e.g., may jeopardize the patient or may require medical/surgical intervention to prevent one of the outcomes listed above)

The terms "severe" and "serious" are not synonymous. Severity refers to the intensity of an adverse event (e.g., rated as mild, moderate, or severe, or according to NCI CTCAE; see Section 5.3.3); the event itself may be of relatively minor medical significance (such as severe headache without any further findings).

Severity and seriousness need to be independently assessed for each adverse event recorded on the eCRF.

Serious adverse events are required to be reported by the investigator to the Sponsor immediately (i.e., no more than 24 hours after learning of the event; see Section 5.4.2 for reporting instructions).

5.2.3 Adverse Events of Special Interest (Immediately Reportable to the Sponsor)

Adverse events of special interest are required to be reported by the investigator to the Sponsor immediately (i.e., no more than 24 hours after learning of the event; see Section 5.4.2 for reporting instructions). Adverse events of special interest for this study are as follows:

- Cases of potential drug-induced liver injury that include an elevated ALT or AST in combination with either an elevated bilirubin or clinical jaundice, as defined by Hy's Law (see Section 5.3.5.8)
- Suspected transmission of an infectious agent by the study drug, as defined below

Any organism, virus, or infectious particle (e.g., prion protein transmitting transmissible spongiform encephalopathy), pathogenic or non-pathogenic, is considered an infectious agent. A transmission of an infectious agent may be suspected from clinical symptoms or laboratory findings that indicate an infection in a patient exposed to a medicinal product. This term applies only when a contamination of the study drug is suspected.
- Suspected infusion related reactions or hypersensitivity reactions, including anaphylaxis, within 24 hours of infusion
- MACE, including:
 - Death due to primary cardiovascular causes (cardiac arrest secondary to progression of disease is excluded)

- Non-fatal myocardial infarction or acute coronary syndrome
- New or worsening heart failure (new globally decreased left ventricular ejection fraction on transthoracic ECHO)
- Grade ≥ 3 dermatologic reactions (as described in Section 5.1.3.3)

5.3 METHODS AND TIMING FOR CAPTURING AND ASSESSING SAFETY PARAMETERS

The investigator is responsible for ensuring that all adverse events (see Section 5.2.1 for definition) are recorded on the Adverse Event eCRF and reported to the Sponsor in accordance with instructions provided in this section and in Sections 5.4–5.6.

For each adverse event recorded on the Adverse Event eCRF, the investigator will make an assessment of seriousness (see Section 5.2.2 for seriousness criteria), severity (see Section 5.3.3), and causality (see Section 5.3.4).

5.3.1 Adverse Event Reporting Period

Investigators will seek information on adverse events at each patient contact.

All adverse events, whether reported by the patient or noted by study personnel, will be recorded in the patient's medical record and on the Adverse Event eCRF.

After informed consent has been obtained but prior to initiation of study drug, only serious adverse events caused by a protocol-mandated intervention (e.g., invasive procedures such as biopsies, discontinuation of medications) should be reported (see Section 5.4.2 for instructions for reporting serious adverse events).

After initiation of study drug, all adverse events will be reported until the study completion/discontinuation visit.

Instructions for reporting adverse events that occur after the adverse event reporting period are provided in Section 5.6.

5.3.2 Eliciting Adverse Event Information

A consistent methodology of non-directive questioning should be adopted for eliciting adverse event information at all patient evaluation timepoints. Examples of nondirective questions include the following:

"How have you felt since your last clinic visit?"

"Have you had any new or changed health problems since you were last here?"

5.3.3 Assessment of Severity of Adverse Events

The adverse event severity grading scale for the NCI CTCAE (v5.0) will be used for assessing adverse event severity. Table 4 will be used for assessing severity for adverse events that are not specifically listed in the NCI CTCAE.

Table 4 Adverse Event Severity Grading Scale for Events Not Specifically Listed in NCI CTCAE

Grade	Severity
1	Mild; asymptomatic or mild symptoms; clinical or diagnostic observations only; or intervention not indicated
2	Moderate; minimal, local, or non-invasive intervention indicated; or limiting age-appropriate instrumental activities of daily living ^a
3	Severe or medically significant, but not immediately life-threatening; hospitalization or prolongation of hospitalization indicated; disabling; or limiting self-care activities of daily living ^{b, c}
4	Life-threatening consequences or urgent intervention indicated ^d
5	Death related to adverse event ^d

NCI CTCAE = National Cancer Institute Common Terminology Criteria for Adverse Events.

Note: Based on the most recent version of NCI CTCAE (v5.0), which can be found at:

http://ctep.cancer.gov/protocolDevelopment/electronic_applications/ctc.htm

- ^a Instrumental activities of daily living refer to preparing meals, shopping for groceries or clothes, using the telephone, managing money, etc.
- ^b Examples of self-care activities of daily living include bathing, dressing and undressing, feeding oneself, using the toilet, and taking medications, as performed by patients who are not bedridden.
- ^c If an event is assessed as a "significant medical event," it must be reported as a serious adverse event (see Section 5.4.2 for reporting instructions), per the definition of serious adverse event in Section 5.2.2.
- ^d Grade 4 and 5 events must be reported as serious adverse events (see Section 5.4.2 for reporting instructions), per the definition of serious adverse event in Section 5.2.2.

